#### **4.4.7 Tanner Staging**

Tanner staging will be determined at the baseline visit in all patients aged from 9-17 years of age and yearly thereafter.

#### **4.4.8 Laboratory, Pharmacokinetic, Biomarker, and Other Biological Samples**

Laboratory safety tests will be collected at timepoints specified in the Schedule of Assessments ([Appendix 1](#)) and analyzed by a central laboratory. For safety monitoring purposes, the investigator must review, sign, and date all laboratory safety tests results.

Additional blood or urine samples may be taken at the discretion of the investigator if the results of any test falls outside the reference ranges, or clinical symptoms necessitate additional testing to monitor patient safety.

Samples for the following laboratory tests will be sent to one or several central laboratories for analysis:

- Hematology (WBC count, RBC count, hemoglobin, hematocrit, platelet count, differential count [neutrophils, eosinophils, basophils, monocytes, and lymphocytes])
- Blood chemistry: AST, ALT,  $\gamma$ -glutamyl transferase, creatine kinase, total and direct bilirubin, alkaline phosphatase (ALP), albumin, creatinine, urea, total protein, sodium, chloride, calcium, phosphorus, potassium, glucose, and additionally in adults and adolescents only, brain natriuretic peptide.
- Coagulation (INR, aPTT, PT).
- Lipids (cholesterol, low-density lipoprotein (LDL) cholesterol, high density lipoprotein (HDL) cholesterol, triglycerides)
- Urinalysis: a midstream, clean-catch urine specimen will be collected for dipstick analysis of protein, blood, glucose and pH. If there is a clinically significant positive result, urine will be sent to the laboratory for microscopy and culture. If there is an explanation for the positive dipstick result, it should be recorded, and there is no need to perform laboratory for microscopy and culture.
- Hormones

Patients aged 6-17 years: thyroid hormones (free thyroxine T4 and thyroid stimulating hormone).

Female patients aged 12-17 years or younger who have menses: estradiol, follicle stimulating hormone, luteinizing hormone.

- Pregnancy test

All women of childbearing potential ( $\leq$ 12 months of non-therapy-induced amenorrhea) or not surgically sterile will have urine pregnancy tests performed at all visits. If a urine pregnancy test is positive, it must be confirmed by a serum pregnancy test.

- Plasma samples for PK analysis

A blood sample will be collected at timepoints specified in the Schedule of Assessments ([Appendix 1](#)). The time of the assessment will be recorded. If PK samples have been missed or taken in error, reasons for these discrepancies must be provided.

Actual date and time of the administration for the preceding two doses (except on V1) and the dosing date and time on the day of assessment must be documented in the eCRF. The most frequent time of drug intake (i.e., with evening, noon, or morning) in the weeks prior to the visit should also be recorded in the eCRF.

Laboratory kits will be provided for all central laboratory assessments. The procedures for the collection, handling, storage and shipping of samples will be detailed in the laboratory manual.

#### **4.4.8.1 Biomarker Assessments**

The following biomarker assessments will be performed as detailed in the Schedule of Assessments ([Appendix 1](#)). *All biomarker samples will be destroyed no later than 5 years after the date of the final clinical study report.*

##### **4.4.8.1.1 SMN Protein Levels**

Whole blood for SMN protein analysis will be collected from every patient.

##### **4.4.8.1.2 In Vivo Splicing of SMN2 mRNA**

Two whole blood samples will be taken from every patient at the timepoints specified in the Schedule of Assessments ([Appendix 1](#)) to measure the relative amounts of *SMN1*, *SMN2-FL*, and *SMNΔ7* mRNA transcript during the course of the study. In addition, housekeeping genes for the quantitative analysis of RNA will be measured. Additional mRNA may be used for exploratory analysis/assay development related to SMA, including, but not limited to, pathways related to SMN function, SMA disease severity, progression, and treatment response.

##### **4.4.8.1.3 Fluid Biomarkers**

The following fluid biomarker samples will be used to assess treatment response in patients. Serum for the analysis of biomarkers related to SMA or to the response from treatment (e.g., muscle damage or insulin-like growth factor system) will be collected.

These samples will be destroyed no later than 5 years after the date of *the final clinical study report* and may be used for additional exploratory analysis/assay development related to SMA including, but not limited to, pathways related to SMN function or treatment response.

#### **4.4.8.2 Clinical Genotyping Samples**

A mandatory whole blood sample will be taken for DNA extraction from every patient at *three timepoints, as indicated in the Schedule of Assessments (see [Appendix 1](#))*. The *baseline* DNA will be used to determine the copy number of SMN2 and may also be used to confirm the SMN1 mutation or deletion. *The baseline and longitudinal DNA samples may be used for additional exploratory analysis/assay development related to SMA including, but not limited to, mitochondrial DNA levels and genes related to SMN function (especially genetic modifiers of SMA, SMN mRNA splicing, or SMN protein*

*expression), which might be dynamically changed due to disease severity, progression, and treatment response.*

These samples will be destroyed no later than 5 years after the date of *the* final clinical study report. The procedures for the collection, handling, storage and shipping of samples will be detailed in the laboratory manual.

Data arising from clinical genotyping will be subject to the confidentiality standards described in Section 8.4.

#### **4.4.8.3 Order of Sample Collection**

Should the total blood volume to be collected at any timepoint according to this Schedule of Assessments exceed 1mL/kg or the volume collected over any 8-week period throughout the study exceeds 4 mL/kg, the blood sample prioritization described below should be followed:

- Any safety laboratory samples (scheduled or unscheduled and performed at the discretion of the investigator);
- PK samples;
- SMN protein levels
- In vivo splicing of SMN2 mRNA
- Clinical genotyping
- Fluid biomarkers assessing treatment response
- RCR samples if collected

#### **4.4.8.4 Spinal Muscular Atrophy Digital Biomarkers**

*Each patient will receive a preconfigured smartphone at the first visit after Protocol BN29854, Version 4 has been initiated and after the new Informed Consent Form has been signed. The device and software will be used to regularly assess motor behavior, as well as to intermittently answer questions related to health and activities associated with routine daily living. The smartphone must be returned to the clinical site in case of study withdrawal, end of the study, or upon request.*

#### **Digital Biomarker Remote Monitoring**

*Patients will be provided with and trained on the device. During the study, patients will be instructed to conduct "Active Tests" every day, at approximately the same time (ideally in the morning after breakfast). The "Active Test" consists of a short, preconfigured sequence of tasks that assess motor symptoms.*

*Device sensor data will be recorded continuously throughout the "Active Tests." Audio will only be recorded during the sustained phonation test. Data are encrypted and uploaded to secure servers whenever the smartphone is connected to WiFi.*

### **Digital Biomarker In-Clinic Assessments**

*Patients will be instructed to bring the smartphone to every clinic visit to check adherence and the technical status of the device.*

*At selected clinic visits, patients will be asked to conduct the “Active Tests” tasks under the supervision of a person trained on the digital biomarker approach.*

*The smartphone must be returned to the clinic in cases where the patient does not meet eligibility criteria, study withdrawal, end of the study, or upon request.*

*At the end of the study or at the time when the subject has completed the study, patients will be asked to complete a pen and paper satisfaction survey on their experience using the smartphone during the study.*

*Additional details are available in the SMA Digital Biomarker Manual.*

### **4.4.9 Electrocardiograms**

ECGs recordings will be performed at the time-points specified in the Schedule of Assessments ([Appendix 1](#)). *If a patient performs a 24-hour Holter ECG as part of the dose increase per Protocol BN29854, Version 4 on a regular visit (see Option 2 in Section 3.1.1.4) and an ECG assessment is scheduled at this regular visit, only the 24-hour Holter ECG will be performed.* All ECG recordings will be performed using a standard high-quality, high-fidelity digital electrocardiograph machine equipped with computer-based interval measurements. Lead placement should be as consistent as possible. ECG recordings must be performed after the patient has been resting for at least 10 minutes. Circumstances that may induce changes in heart rate, including environmental distractions (e.g., television, radio, conversation) should be avoided during the pre-ECG resting period and during ECG recording.

For safety monitoring purposes, the investigator must review, sign, and date all ECG tracings. Paper copies of ECG tracings will be kept as part of the patient's permanent study file at the site. ECG tracings should also be submitted to a central laboratory. Results will be provided to sites within 72 hours or 48 hours if any signal is detected.

#### **4.4.9.1 24-Hour Holter ECG Monitoring**

*All patients who have consented to the 10 mg/kg BID dose increase will be requested to have 24-hour Holter ECG monitoring (see Section 3.1.1.4) before the dose increase and 4 weeks after the dose increase. The Holter ECG monitor will be placed on the patient at the dose increase visit and at the dose increase safety follow-up visit. After the first predose 24-hour Holter ECG monitoring at the dose increase visit, patients will return the Holter ECG monitor to the site at the dose increase safety follow-up visit (at the latest). After the second 24-hour Holter ECG monitoring, which is performed at the dose increase safety follow-up visit, the recording data must be sent to the central laboratory, and the site will be informed of the results within 1 week. Any abnormality*

*in the Holter ECG data will be assessed on a case-by-case basis between Sponsor and investigator, and appropriate measures will be taken as needed.*

#### **4.4.10 Patient-Reported Outcomes**

Patient Reported Outcomes (PRO) data will be collected via questionnaires to more fully characterize the clinical profile of olesoxime. The questionnaires will be in paper format, and translated as required in the local language. To ensure instrument validity and that data standards meet health authority requirements, the questionnaires scheduled for administration during a clinic visit should be completed *after the laboratory safety samples have been taken and prior to administration of study treatment and to the performance of non-PRO assessments, in the order defined below. Where appropriate, both caregiver and patient should complete the PedsQL Generic Core Scales. The self-report version of EQ-5D-5L should be completed by patients ≥12 years of age, and the proxy version completed by caregivers of patients <12 years of age. The SMAIS self-report version should be completed by patients aged ≥12 years, and the SMAIS caregiver-report version should be completed by a caregiver for all patients, where possible. The form used in the baseline assessment should be used at all subsequent visits and the dose increase visit (e.g., patients aged <12 years will not complete the EQ-5D-5L or the SMAIS even if their 12th birthday occurs during the study, and patients aged 8-12 years will continue to use the PedsQL forms for ages 8-12 years even if their 13th birthday occurs during the study).*

The PRO measures for this study are as follows:

- *The EQ-5D-5L conducted at all visits except screening, Visit 2, and Visit 4: The EQ-5D-5L is a self-report health status questionnaire that consists of six questions used to calculate a health utility score for use in health economic analysis (EuroQol Group 1990; Brooks 1996; Herdman et al. 2011; van Hout et al. 2012; Janssen et al. 2013, Oppe et al. 2014). There are two components to the EQ-5D-5L: a five-item health state profile that assesses mobility, self-care, usual activities, pain/discomfort, and anxiety/depression, as well as a visual analog scale (VAS) that measures overall health status. Published weighting systems allow for creation of a single summary score. Overall scores range from 0 to 1, with low scores representing a higher level of dysfunction; for some countries (e.g., United Kingdom), scores below zero are possible. The EQ-5D-5L will be utilized in this study for economic modeling.*

*Patients who participate in the digital biomarker assessment will also complete an electronic version of the EQ-5D-5L every 2 weeks.*

- *The PedsQL Generic Core Scales (Version 4.0) and PedsQL Neuromuscular Module (Version 3.0) conducted at all visits, with the exception of screening, Visit 2, and Visit 4.*

The PedsQL is a modular instrument designed to measure health-related quality of life and disease-specific symptoms. The instrument integrates generic core scales and disease-specific modules into a single measurement system (a full listing of peer-reviewed journal publications is available at [www.pedsql.org](http://www.pedsql.org)). The PedsQL Generic Core Scales (*Version 4.0*) and *PedsQL Neuromuscular Module (Version 3.0)* have been shown to be feasible, reliable, and valid in the SMA population ([Iannaccone et al. 2009](#)).

The PedsQL Generic Core Scales (*Version 4.0*) includes 23 items that can be completed in around 4 minutes, using self-report (ages 5+) and/or parent report (ages 5+). The instrument covers physical, emotional, social, and school functioning and can be summarized into three main scores (total scale score, physical health score, and psychosocial health score).

The PedsQL Neuromuscular Module (*Version 3.0*) includes 25 items that can be completed in around 4 minutes, using self-report (ages 5–18) and/or parent report (ages 5–18). The instrument covers problems related to neuromuscular disease, communication and family resources and can be summarized into total and domain scores.

For all PedsQL items, the recall period will be the past one month. PedsQL assessments will be performed using both parent report and child report where possible, dependent on age and ability to complete the questionnaire. An administrator is also required to develop rapport with respondents, emphasize the importance of the questionnaire, address concerns, and ensure accurate completion and confidentiality. Age bands for the instrument are as follows, and within a scale or module, the appropriate age band should be used based on the age of the patient at *enrollment*:

- Young child (5–7 years)
- Child (8–12 years)
- Teen (13–18 years)
- Young Adult (18–25 years) [Core scales only]
- Adult (>25 years) [Core scales only]

For scoring purposes, scale items are linearly transformed to a 0–100 scale (0=100, 1=75, 2=50, 3=25, and 4=0) so that higher scores indicate better health-related quality of life. Scale scores are computed as the sum of the items divided by the number of items which were answered. It is recommended that if more than 50% of the items in the scale are missing, the scale score should not be computed.

- *The SMAIS was developed specifically for SMA in order to assess function-related independence. The SMAIS contains 29 items, assessing the amount of assistance required from another individual to perform daily activities, such as eating or transferring to/from a wheelchair. Each item is scored on a 0–4 scale (with an additional option to indicate that an item is non-applicable). Item scores are summed to create the total score. Lower scores indicate greater dependence on another individual. The SMAIS will be completed by patients aged ≥12 years. The*

*SMAIS will be conducted at all visits including the dose increase visit, with the exception of screening, Visit 2, and Visit 4.*

*The PROs should be completed in the following order (caregivers should also follow this order when completing these questionnaires about the patient):*

1. SMAIS
2. EQ-5D-5L
3. PedsQL Neuromuscular Module
4. PedsQL Generic Core Scale

#### **4.4.11 Caregiver-Reported Outcomes**

As noted above, caregivers will be required to complete questionnaires assessing the impact of disease on the patient. For the EQ-5D-5L Proxy and the PedsQL Generic Core Scale and Neuromuscular Module, the questionnaires should be completed by the primary caregiver of the patient. For adult patients who do not receive care from their parents (or other individuals close to the patient), the collection of caregiver-reported outcomes is not mandatory; however, it has to be fully documented in the appropriate eCRF form.

Caregiver Reported Outcomes data will be collected via questionnaires to understand the impact of disease on the caregiver. The questionnaires will be in paper format, and translated as required in the local language, and should be completed by the same caregiver throughout the study. Written informed consent must be obtained from the caregiver. In case the patient is an adult who does not receive care from a relative, partner, or close friend (i.e., someone who is not necessarily a professional caregiver), the collection of caregiver-reported outcomes is not mandatory; however, it has to be fully documented in the appropriate eCRF form. The caregiver-reported outcome measures for this study are as follows:

- Caregiver resource use: WPAI:CG, conducted at all visits, with the exception of screening, Visit 2, and Visit 4
  - Occupational work productivity and activity impairment in caregiver will be assessed using the WPAI:CG. The WPAI:CG consists of 6 questions about the effects of SMA on the following: employment status; hours missed due to patient caregiving; hours missed due to other reasons; hours actually worked; and two questions that measure the degree to which health problems affected productivity due to caregiving (presenteeism) and regular daily activities.
- Caregiver generic health-related quality of Life *SF-36v2*, conducted at all visits, with the exception of screening, Visit 2, and Visit 4
  - SF-36v2* is widely used across databases and is a well-established generic scale with 36 questions grouped into eight domains *and two summary scores* covering aspects of functioning and physical and mental health in caregiver.

The same caregiver should complete the assessments at all specified visits (e.g., it is not permitted for the mother of one patient to complete an assessment at one visit, and for the father of the same patient to complete the same assessment at a subsequent visit).

#### **4.4.12 Clinical Global Impression of Change**

*The CGI-C is a single-item measure of change in global health that uses seven response options: Very Much Improved, Much Improved, Minimally Improved, No Change, Minimally Worse, Much Worse, and Very Much Worse. It is a widely used endpoint in clinical trials across a variety of disease areas. Clinicians will score patients using this scale based on their impression of change in the patient's global health since baseline. To enhance inter-rater consistency, an instructions document (developed with input from clinical experts) will be provided, which includes examples for each of the response options.*

*The same clinician should complete the CGI-C at all specified visits for an individual patient. The CGI-C will be administered at the dose increase visit and study Visits 5, 6, and 7.*

#### **4.4.13 Olesoxime Fatigability Survey**

*The OFS is a brief survey designed to explore potential benefit of olesoxime on fatigability (i.e., endurance). This survey will be completed once, at the dose increase visit. The data will be used to aid assessment of options for further clinical development of olesoxime. The survey will be completed by clinicians following discussions with the patient and their family/caregivers.*

#### **4.4.14 SMA Disease Specific Assessments**

##### **4.4.14.1 Motor Function Measure (MFM)**

The MFM ([Berard et al. 2005](#)) is an ordinal scale constructed for use in patients with neuromuscular disorders, and has been validated in SMA. The scale evaluates motor function in three dimensions:

- D1: evaluates functions related to standing and transfer,
- D2: evaluates axial and proximal function in supine and sitting position on mat and chair,
- D3: evaluates distal motor function.

The scoring of each task uses a 4-point Likert scale based on the patient's maximal abilities without assistance: 0, cannot initiate the task or maintain the starting position; 1, performs the task partially; 2, performs the task incompletely or imperfectly (with compensatory/uncontrolled movements or slowness); and 3, performs the task fully and "normally." The scores are summed to yield a total score expressed as the percentage of the maximum possible score (the one obtained with no physical impairment); the lower the total score, the more severe the impairment. The MFM is free and available in most

common European languages. Users' manual and scoring sheet will be provided to the sites prior to study start.

#### **4.4.14.2      Forced Vital Capacity (FVC)**

Pulmonary Function will be assessed in patients 5 years or older by measuring forced expiratory vital capacity (FVC) (as percent predicted for age and height). Pulmonary measures have been validated in SMA ([Iannaccone et al. 2003](#)). If height cannot be measured (e.g., with scoliosis or contractures), ulna length will be used to calculate a surrogate height measure.

#### **4.4.15      Unscheduled Visits**

Patients reporting new or worsening symptoms related to either the natural course of the disease or an adverse event should be seen at the investigational site, if deemed appropriate by the treating physician. Assessments performed at unscheduled visits will depend on the clinical needs of the patient.

Any unscheduled visits and procedures should be recorded in the eCRF.

#### **4.4.16      Early Discontinuation Visit**

Patients who decide to discontinue study treatment will be asked to return to the clinic for an early discontinuation visit 28 ( $\pm$  5) days after last dose, regardless of reason of discontinuation (*safety follow-up, as described in Section 3.1.1.5*).

Remaining IMP delivered to the patient should be returned to the trial site during this visit.

#### **4.4.17      Treatment Completion**

Patients will be asked to come for a final study visit as early as possible but not later than 6 weeks after the end of the study at the patient's site (as described in Section 3.2).

If a patient had a regular visit prior to up to 3 months before announcement of the study end the last regular visit will be regarded as the final visit. However, remaining IMP delivered to the patient should be returned to the trial site within 6 weeks of announcement of study end.

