##### **3.1.1.5 Safety Follow-Up**

*Patients who withdraw from study drug treatment during the open-label period of the study will be observed for a period of 28 days after last dose.*

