## **3.2 END OF STUDY**

*The study will continue until olesoxime is commercially available in the patient's country, or as per local regulation, or per the Sponsor's decision to terminate the olesoxime*

program for SMA, but will not exceed 4 years after the last patient was enrolled in the study.

**NB** In the UK, the study will last for a fixed period of 3 years.

The end of this study is defined as the date when the last patient, last visit (LPLV) of the treatment period occurs.

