### **5.3.1 Adverse Event Reporting Period**

Investigators will seek information on adverse events at each patient contact. All adverse events, whether reported by the patient or noted by study personnel, will be recorded in the patient's medical record and on the Adverse Event eCRF.

**After informed consent** has been obtained **but prior to initiation of study drug**, only serious adverse events caused by a protocol-mandated intervention (e.g., invasive procedures such as biopsies, discontinuation of medications) should be reported (see Section 5.4.2 for instructions for reporting serious adverse events).

**After initiation of study drug**, all adverse events will be reported until 28 days after the last dose of study drug. After this period, the investigator should report any serious adverse events that are believed to be related to prior study drug treatment (see Section 5.6).

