2.3 ANALYSIS TIMING

The final analysis will be performed on all data collected up to the end of the study, after the last patient has completed the last follow-up visit.

Interim analyses of the data may be performed prior to final database lock to adapt to information that may emerge during the course of the study or for submissions to health authorities.

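### End-of-study safety follow-up: Protocol 3.1.1.5 and 4.4.17 do not match Appendix 1 on who gets the post-dose contact and the completion visit, and that contact may fall before the 28-day AE window closes

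*Protocol*

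**What the plan says.** **Final visit.** Protocol 4.4.17 asks for a final visit within 6 weeks of study end at the patient's site. It then makes an exception for a patient seen at a regular visit in the 3 months before the announcement: "the last regular visit will be regarded as the final visit". For that patient the only remaining duty it names is drug return: "remaining IMP delivered to the patient should be returned to the trial site within 6 weeks of announcement of study end". No date of last dose is tied to the announcement. Footnote e of Appendix 1 asks for a completion visit within the same 6 weeks but does not carry the 3-month exception.

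**Post-dose follow-up.** Protocol 3.1.1.5, the section headed Safety Follow-Up, reads: "Patients who withdraw from study drug treatment during the open-label period of the study will be observed for a period of 28 days". Section 4.4.16 adds a clinic visit 28 (± 5) days after last dose for patients who discontinue. Appendix 1 has a separate Safety Follow-Up column, also 28 (± 5) days after last dose, with the adverse events row marked. Footnote f says this contact is by phone, with a visit only if the investigator thinks one is needed. Neither the column nor the footnote is limited to withdrawers.

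**AE window.** Protocol 5.3.1 applies to everyone who has started drug: "all adverse events will be reported until 28 days after the last dose of study drug". It also tells investigators to ask about AEs at every patient contact.

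**The concern.** When the sponsor closes the study, every patient still on drug leaves as a completer. For these patients the body of the protocol and the schedule give different instructions on two matters: whether a completion visit is always due, and whether a contact is due 28 days after last dose. A site that reads 3.1.1.5 and 4.4.17 literally could accept an earlier visit as final, collect the remaining drug and make no post-dose contact. A site that reads Appendix 1 would do both. Safety is the primary objective, and one listed reason for termination is a safety hazard (4.5.3), so AE collection at the end of treatment should not depend on which page the site consults.

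The ± 5 window raises a separate problem that affects all patients: the last planned AE enquiry can take place before the period it is meant to cover has ended.

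**Working it through.** There is no sample-size or power figure to reproduce. The check consists of setting the passages side by side and counting days.

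**1. Who gets the post-dose contact?**
- 3.1.1.5: withdrawers from drug only.
- 4.4.16: patients who discontinue treatment (clinic visit).
- Appendix 1, Safety Follow-Up column and footnote f: no restriction. The adverse events row has 16 cells for 16 columns and only screening is blank, so the Safety Follow-Up cell is marked.
- 5.3.1: AE reporting to day 28 for everyone.

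The schedule and 5.3.1 agree with each other. Section 3.1.1.5 is narrower than both.

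**2. Is a completion visit always due?** Under footnote e, yes, within 6 weeks. Under 4.4.17, not for a patient seen in the preceding 3 months. The two conflict.

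**3. Time on drug after the accepted final visit.** Take that visit as day 0. Inputs: 3 months ≈ 91 days (89 to 92, depending on the calendar) and drug-return limit 6 weeks = 42 days, both from 4.4.17. Because no last-dose date is stated, both ends of the range are shown for a visit the full 3 months before the announcement.

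| Assumption | Last dose | AE window ends (+28) | Contact at 28 ± 5 |
|---|---|---|---|
| Dosing stops at announcement | day 91 | 91 + 28 = day 119 | days 114 to 124 |
| Dosing runs to return limit | 91 + 42 = day 133 | 133 + 28 = day 161 | days 156 to 166 |

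With 89 to 92 days for 3 months, the last dose is at day 89 to 92 or day 131 to 134, and the AE window ends between day 117 and day 162. A more recent visit shortens all of these. The routine interval after Visit 5 is 26 × 7 = 182 days.

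**4. The 12-week phone call.** After Visit 5 a call is due 84 ± 7 days after each visit, that is, on days 77 to 91. If the visit was 91 days before the announcement, the call falls on or before the announcement and should have been made. If the visit was less than 77 days before, the call falls after the announcement, and the text does not say whether it is still made.

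**5. How many patients?** With visits every 182 days, evenly spread relative to the announcement (an assumption), 91/182 = one half of those remaining would have a visit inside the 3-month window. The wording of 3.1.1.5 leaves out all completers, whether or not their visit falls in that window.

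**6. The contact window.** 28 − 5 = day 23. A contact on day 23 complies, and days 24 to 28 then lie inside the 5.3.1 window with no later planned enquiry.

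**The case against.** The strongest reply is that the contact already exists. Appendix 1 schedules it, footnote f describes it, and neither limits it by exit route. Withdrawers already have a clinic visit at the same time, so a phone column meant only for them would be largely redundant. Protocol 3.1.1 makes safety follow-up a period of the whole study. This stands: a reader might infer from 3.1.1.5 that completers have no assured safety contact, and the documents do not support that. What does not follow is that the text is sound, because the section that defines the follow-up still leaves completers out.

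It is also fair that 133 days without a clinic visit is shorter than the routine 182, and that ECGs are yearly after Visit 2 in any case (footnote v). The gap is not unusual for this study; it matters because it falls at the end of treatment, with no later visit to close it.

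The ± 5 window may be called an ordinary operational choice, since the duty to report to day 28 remains. The duty does remain, but a planned enquiry on day 23 cannot serve days 24 to 28.

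Three further inferences are tempting and do not hold:
- **Event rates are biased low.** SAP 4.4.2.4 counts risk time to 28 days after completion, but only for the rate of SMA-related events, and the direction is not fixed. If completion means the earlier accepted visit, later time on drug may leave the denominator while its events are still counted, which would raise the rate.
- **Most of the cohort, or up to 171 patients, is affected.** 171 is the maximum enrolment, not the number on drug at study end, and the visit exception reaches about half of those remaining under even spacing.
- **Protocol 3.2 conflicts with SAP 2.3.** The first defines study end: "The end of this study is defined as the date when the last patient, last visit (LPLV) of the treatment period occurs". The second times the final analysis, "after the last patient has completed the last follow-up visit". Both can be true, and 3.2 need not be redefined.

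**Conclusion.** The point holds as an internal contradiction with a modest practical consequence. Section 3.1.1.5 is narrower than Appendix 1 and 5.3.1 on who is followed after last dose, and 4.4.17 carries an exception that footnote e lacks. A site following the body text could omit the post-dose contact for completers, and any site may make its last planned AE enquiry up to 5 days before the window closes.

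For patients whose earlier visit is accepted as final, no in-person safety assessment is assured for up to about 91 days on drug if dosing stops at the announcement, or up to about 133 days if it continues to the drug-return limit. The second figure rests on an assumption, because no last-dose date is given. The share of one half rests on evenly spread 26-week visits. This is more than missing detail, because the conflicting texts lead to different data collection, but it does not show that completers are left without any scheduled safety contact.

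**What to change.** 1. Reword 3.1.1.5 to cover patients who withdraw from or complete study drug, so that the footnote-f phone contact explicitly applies to all, including those whose earlier visit is accepted as final under 4.4.17.
2. Record the date of last dose at that contact, so that the AE window can be fixed for each patient.
3. Change the contact window from 28 (± 5) days to 28 days (0 to +5) after last dose. The earliest date moves from day 23 to day 28; the latest stays at day 33.
4. Reconcile 4.4.17 with footnote e so that both state the same rule on when a completion visit is due. Which rule to adopt is for the sponsor to decide.

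The cost is protocol wording, one already scheduled call per completing patient, and a slightly later last contact where sites would have called early.
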